Prior to the analysis of the final study data, a detailed Statistical Analysis Plan (SAP) will be written describing all analyses that will be performed. The SAP will contain any modifications to the analysis plan described below.

Data Sets Analyzed

Initial analyses will evaluate group differences on demographic and baseline variables, will use contingency tables with chi-square testing, ANOVA's, and examination of correlations between baseline variables subjective responses and clinical results. General data analysis procedures: Urn randomization will be used for gender to reduce any potential between-group differences (lorcaserin vs. placebo) on baseline variables. Prior to data analysis procedures, groups will be examined for differences in other baseline characteristics that could potentially influence treatment outcome. Any variables that differ between groups and are related to outcome measures will be examined as potential covariates in subsequent data analyses.

Demographic and Baseline Characteristics

Women, minorities, and children (18-21 years of age) will be included to the extent they are reflected in this non-treatment seeking population. In our previous cocaine clinical trials, the percentage of females and males is approximately 30% and 70% respectively. We will continue recruitment efforts to achieve a 50-50 balance and thus permit meaningful analyses by sex across groups.

The ethnic representation has been 55% Black, 44% White, 15% Hispanic, and <1% Asian in previous research by our group. Nevertheless, we are prepared to implement recruitment procedures to ensure a more diverse patient population. These procedures include: 1) Targeted advertising in newspapers which serve minority communities (e.g., Hispanic or Latino communities). 2) Distribution of flyers and notices in neighborhoods known to have a high minority population. 3) Engaging in outreach activities on an ongoing basis, e.g.,

contacting church and community leaders in the Hispanic communities to provide educational material about cocaine dependence and its consequences; providing contact information to aid in referrals to our clinic.

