Children as defined by NIH (age 18-21 years) will be included in this research. The incidence of severe cocaine abuse/dependence is relatively small in the population of youth less than 18 years old. From a safety perspective, risks of exposure to the proposed study medication and cocaine administration in substance-dependent children under 18 have not been established.

Analysis of Primary Endpoint

1. Safety: Heart rate (HR) and blood pressure (BP) measures during saline infusions will be compared to HR and BP after each cocaine infusion (20 mg and 40 mg doses). Changes in HR and BP induced by cocaine infusion along with lorcaserin will be compared to those without lorcaserin, by cocaine dose level (20 mg and 40 mg doses), using repeated measures analysis of variance (ANOVA). Changes in ECG readings during saline infusion as compared to those taken during cocaine infusions will be reported as summary statistics. Adverse event data will be compiled for lorcaserin and placebo cohorts and presented as summary statistics.
2. Cocaine Self-administration: Repeated measures ANOVA with cocaine dose (0mg, 25mg) and lorcaserin dose (0mg, 10mg, 20mg) as within subject factors will be used to examine differences in mean cocaine choice selection. In addition, a Bayesian analysis will be carried out as described below.
3. Subjective response to cocaine: Subjective response measures (VAS) obtained during saline infusions will be compared between lorcaserin and placebo subjects to those during cocaine infusions by cocaine dose level to determine the extent to which these measures are modified by the administration of lorcaserin using repeated measures ANOVA.
4. Cocaine PK: Plasma concentration-time profiles of cocaine after cocaine infusion during placebo administration (Day 2) will be analyzed to obtain pharmacokinetic parameter estimates of cocaine (Tmax, AUC, apparent t_{1/2}, CL) by individual. These parameters will be compared within subjects on sessions with lorcaserin (Day 6 and 10).

Analysis of Secondary Endpoints

Response inhibition: Commission errors on the IMT will be compared between lorcaserin and placebo subjects to determine the extent to which this measure is modified by the administration of lorcaserin using repeated measures ANOVA.

Safety and tolerability data will be summarized by treatment group.

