Adverse event rates will be coded by body system and MedDra classification term. Adverse events will be tabulated by treatment group and will include the number of patients for whom the event occurred, the rate of occurrence, and the severity and relationship to study drug.

Interim Analysis

When approximately 50% of patients have completed the study, an interim analysis for safety will be conducted by the DSMB. Serious adverse events will be monitored by the committee on an ongoing basis throughout the study.

Sample Size and Randomization

This project requires a final sample size of 18 subjects (Six subjects assigned to Group A (placebo) and 12 subjects assigned to Group B (active lorcaserin)). This sample size for effect of lorcaserin on cocaine self-administration was based on previous research showing effects of medication on human cocaine self-administration (Hart et al, 2008). In an effort to increase the power of the study, a Bayesian approach will also be utilized that incorporates information from previous studies. This approach will use a Bayesian hierarchical model with subject at the lowest level of the hierarchy and treatment group at the second level. This model is analogous to the repeated measures ANOVA except that prior information will be introduced. Since many similar studies have been conducted with cocaine users and the same outcome measures we will assign an

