informative prior distribution on the control group where the mean and standard deviation are educated guesses from the information provided in previous study of Hart et al. (2008). For the treatment group we will assume a priori no change in the mean from the control group and the standard deviation are similar to those as the experimental group of the study by Hart et al. (Hart et al, 2008). The model will be calculated using standard Markov Chain Monte Carlo (MCMC) packages such as WinBUGS, OpenBUGS, JAGS or MCMCpack in R. Because MCMC sampling techniques are being employed the quality of the samples from the posterior distribution will be checked using trace plots, effective sample size, potential scale reduction factor and Hellinger distances (for more on Bayesian analyses and MCMC sampling see (Gelman et al, 2013). As necessary techniques such as discarding burn-in samples, thinning and over-disperse starting points will be employed in order to obtain a set of samples from the posterior distribution that have an effective sample size of 10,000 on all parameters. All inferences will be made from this set of samples from the posterior distribution.

To calculate the power for the acute effects of the study three analyses are considered using the paired differences of subjects at baseline and acute time points. A two-sample test on the means is performed using: Wilcoxon test (non-parametric), T-test (parametric) and a Bayesian (parametric) approach. While from a

n1	Test	Percent Change				
		Low (10%)	Medium (25%)	High (50%)	75%	100%
4	T-test	0.116	0.448	0.955	0.998	1
	Wilcoxon	0.044	0.242	0.855	0.992	1
	Bayesian	0.249	0.689	0.992	1	1
6	T-test	0.138	0.528	0.981	0.999	1
	Wilcoxon	0.079	0.357	0.941	0.997	1
	Bayesian	0.308	0.782	0.994	1	1
8	T-test	0.116	0.588	0.986	1	1
	Wilcoxon	0.096	0.495	0.956	1	1
	Bayesian	0.309	0.803	0.999	1	1
Wilcoxon and Bayesian Power are based off of 1,000 Monte Carlo simulations.						

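### Covariates are chosen after looking at group differences and outcomes in 6 versus 12 subjects, and neither the outcome's baseline value nor gender is fixed in any between-arm model

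*Combined protocol and SAP*

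**What the plan says.** Data Sets Analyzed, under Statistical Methods and Considerations, sets the rule, and the synopsis repeats it. Initial analyses of group differences "will use contingency tables with chi-square testing, ANOVA's, and examination of correlations between baseline variables subjective responses and clinical results". On randomization: "Urn randomization will be used for gender to reduce any potential between-group differences (lorcaserin vs. placebo) on baseline variables". After that, "groups will be examined for differences in other baseline characteristics that could potentially influence treatment outcome", and then: "Any variables that differ between groups and are related to outcome measures will be examined as potential covariates in subsequent data analyses". The section does not say what counts as a difference or a relation, and it does not list the variables to be screened.

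Analysis of Primary Endpoint and Analysis of Secondary Endpoints name repeated measures ANOVA for heart rate and blood pressure, VAS, cocaine choices and IMT commission errors. None of these descriptions names a covariate. For cocaine choices the model is "Repeated measures ANOVA with cocaine dose (0mg, 25mg) and lorcaserin dose (0mg, 10mg, 20mg) as within subject factors", so the placebo-day session is one level of the response. PK parameters are compared within subjects against Day 2. The power calculation in Sample Size and Randomization works "using the paired differences of subjects at baseline and acute time points".

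A detailed SAP is promised before the final data are analyzed, and it may modify this plan.

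**The concern.** The first condition of the rule needs the group labels and the second needs the outcomes. The model is therefore settled only after both can be seen. With 18 subjects, one extra covariate can move an estimate noticeably, and several variables could pass or fail depending on a threshold that nobody has written down.

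The two covariates with the best claim to a place are not secured. Gender is the urn factor, yet the screen covers only characteristics other than gender, and gender is in no model. A pre-treatment value of each outcome is scheduled for every subject:

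- **Heart rate, blood pressure and VAS:** Day 2, under single-blind placebo.
- **Cocaine choices:** Day 3, before the first evening dose of lorcaserin.
- **IMT:** Day 1.

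None of these is named as a covariate. What is at stake is analyst freedom, plus some precision in a study that says it wants more power.

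**Working it through.** **Inputs from the documents.** 6 placebo and 12 lorcaserin subjects; t-test power in the n1 = 6 row of 0.138, 0.528, 0.981 and 0.999 for 10%, 25%, 50% and 75% change; a site history in which "the percentage of females and males is approximately 30% and 70% respectively".

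**Assumed, because not stated.** Two-sided alpha 0.05; a baseline-outcome correlation ρ of 0.3 to 0.9, with equal variances; one post-treatment value per subject. The SD is not given either, so the effect is worked out from the power table.

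**Step 1: the plan's own figure.** For a two-sample t-test on change scores, df = 16, the critical t is 2.12 and the noncentrality is d × √(6 × 12 / 18) = 2d. Setting power to 0.528 gives d = 1.08 for a 25% change. Scaling d in proportion gives about 0.13, 0.528, 0.982 and 1.000 for the four cells, close to the printed row. A one-sided test fits worse (0.169 in the 10% cell). Some cells for n1 = 4 and n1 = 8 fit less well (for example 0.414 against a printed 0.448), but they are not used here. Because the table rests on paired differences, d = 1.08 is in change-score SD units.

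**Step 2: what a significance screen sees.** A baseline difference reaches p < 0.05 only if it exceeds 2.12 × √(1/6 + 1/12) = 2.12 × 0.5 = 1.06 SD. With 10 independent variables, the chance that at least one does so by luck is 1 − 0.95^10 = 0.40.

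**Step 3: fixed baseline adjustment.** The change-score variance is 2σ²(1 − ρ). The residual variance after baseline adjustment is σ²(1 − ρ²). Their ratio is (1 + ρ)/2, so the effective d is 1.08 × √(2/(1 + ρ)). One df is lost, and the variance of the contrast rises by about 1/15 for chance imbalance in the covariate.

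| ρ | variance ratio | effective d | power, analytic | power, simulated | change-score power |
|---|---|---|---|---|---|
| 0.3 | 0.65 | 1.34 | 0.68 | 0.68 | 0.528 |
| 0.5 | 0.75 | 1.25 | 0.62 | 0.61 | 0.528 |
| 0.7 | 0.85 | 1.17 | 0.57 | 0.56 | 0.528 |
| 0.9 | 0.95 | 1.11 | 0.52 | 0.51 | 0.528 |

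**Step 4: adding gender.** With no gender effect, baseline plus gender gave simulated power of 0.64, 0.57, 0.53 and 0.49 at ρ = 0.3, 0.5, 0.7 and 0.9, about 3 points below baseline alone. Other simulations gave 0.665, 0.610, 0.572 and 0.519, about 1 point or less below baseline alone. A rerun shows that the cost depends on balance: under 1 point if women are split evenly by arm (2 of 6 and 4 of 12), about 3 points if the split is left to chance. With a 0.5 SD gender effect, adding gender to baseline raised power from 0.628 to 0.658 at ρ = 0.3, from 0.580 to 0.617 at 0.5 and from 0.501 to 0.552 at 0.7.

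**Step 5: the rule itself, under one reading.** The screen was simulated with p < 0.05 for both conditions, applied to the baseline value and 10 noise variables. It selected a covariate in about 7% to 10% of trials with an effect. Power was 0.488, 0.484, 0.488 and 0.488 at the four correlations (no gender effect), against about 0.53 for the plain change score. Type I error was 0.042 to 0.045. The threshold and the number of candidates are assumptions.

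**The case against.** The strongest reply is that baseline is already used. The choice model carries the placebo day as a within-subject level, PK is compared within subjects, and power was set on paired differences. This stands. The right comparator is the change-score test at 0.528, and at a correlation of 0.9 adjustment gains nothing over it.

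Several stronger readings are tempting, and the documents do not support them:

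- **Fixed adjustment would lift power to 0.62–0.79.** That range appears if d = 1.08 is applied to raw post-treatment scores and compared with an analysis that ignores baseline. At ρ = 0.7, a change-score d of 1.08 is a raw d of 1.08 × √(2 × 0.3) = 0.84, and adjusted power is about 0.56.
- **Real imbalances go undetected more than half the time.** A true 1 SD difference would be found with 47% power. However, randomization rules out a true difference, so only chance imbalance matters, and the plan fixes no p < 0.05 screen.
- **The rule inflates type I error.** The simulation showed none. It tested one fixed version of the rule, so it cannot speak to free choice among versions.
- **The rule bars baseline and gender.** It does not. It speaks of potential covariates and forbids nothing; it simply fixes neither.

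Two further replies carry some weight. Gender adjustment is not free: 30% of 18 is about 5 women. The urn also rests on the synopsis and Data Sets Analyzed alone, because the section on assigning subjects mentions neither urn nor gender. As for the promised SAP, it need only precede the final analysis. The blind is broken after database lock, so nothing requires the SAP to come before unblinding.

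**Conclusion.** The point holds, at modest size. The plan states a data-dependent covariate rule with no threshold or candidate list, and it fixes neither baseline nor gender as a covariate in any between-arm model. The harm is analyst freedom, which is plain from the text, and some loss of precision. At the 25% effect, fixed baseline adjustment gains about 15 points of power at a correlation of 0.3, 8 at 0.5, 3 at 0.7 and none at 0.9. Gender takes back up to about 3 points if it has no effect. These sizes rest on the assumed correlation, two-sided alpha of 0.05 and a single post-treatment value. The case for prespecification does not depend on them.

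**What to change.** Delete the test-based rule from Data Sets Analyzed and the synopsis. Before unblinding, specify the model for each between-arm comparison: heart rate and blood pressure, VAS, IMT, and any between-arm analysis of cocaine choices. Each should have the post-treatment sessions as the repeated response and two fixed covariates: gender, and the subject's own pre-treatment value of that outcome (Day 2 for heart rate, blood pressure and VAS; Day 1 for IMT; Day 3 for choices). Name any other covariates in advance and use them in sensitivity analyses only. Baseline tables can stay as description. Leave the within-subject PK comparison as it is.

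The cost is SAP wording and one or two degrees of freedom. Any model in which the placebo day is now a repeated-measures level must also be restructured, because that day cannot be both response and covariate. No extra subjects or visits are needed.

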Each pill bottle of study drug will be labeled with the required FDA warning statement, the protocol number, a treatment number, the name of the study physician, and directions for patient use and storage.

Administration of Study Drug

Dosage/Dosage Regimen

If subjects meet inclusion criteria, they will be seen both in the hospital and at IDAS clinic for a total of 12 active study days and monitoring procedures will be in place to detect drug and alcohol use and assess for adverse events at each visit. In addition, the hospital cocaine administration procedures will reduce the likelihood of increased cocaine craving after cocaine administration. Subjects will undergo procedures as described below. Subjects will not be allowed to smoke cigarettes, as smoking is not allowed in the hospital or anywhere on the VCU campus. Subjects will have the option to use a nicotine patch dosed based on the amount of daily cigarettes smoked. Subjects will not be allowed to leave the CRS Unit nor receive visitors during their study visits. Subjects who are unable to comply with these restrictions will be dropped from the study. After a screening cocaine infusion to determine safety, eligible subjects will be randomized to Group A –placebo only or Group B –placebo followed by an ascending dose of lorcaserin. Six subjects will be assigned to Group A (placebo) and 12 subjects will be assigned to Group B (active lorcaserin).

Study Drug Dosage: Lorcaserin will be 10mg once daily increasing to 10mg twice daily.

Outcome Measures: The primary outcome measures are adverse events, cardiovascular responses (Heart rate (HR), blood pressure (BP), ECG measurements, subjective response to cocaine, cocaine self-administration, and cocaine blood PK. Secondary outcome measures will be impulsivity as measured by the immediate memory task (IMT).

- 1) Days 1-2: All subjects will be seen on the CRSU. All subjects will receive placebo on days 1-2 in a single blind fashion. Vital signs including heart rate, blood pressure and respiration rate will be obtained after placebo administration. Days 1-2 will be single-blind placebo, whereas all remaining study days will be double-blind. All subjects will leave the CRSU at the end of each study day.

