2	20 mg Cocaine	0 mg Cocaine	20 mg Cocaine	0 mg Cocaine
3	0 mg Cocaine	20 mg Cocaine	40 mg Cocaine	20 mg Cocaine
4	40 mg Cocaine	40 mg Cocaine	0 mg Cocaine	40 mg Cocaine

Dispensing

Study drugs will be dispensed by the research pharmacist and administered by the research nurse on the CRS unit (cocaine) or trained research personnel (lorcaserin) at IDAS.

Supply of Study Drug at the Site

Study drug will be provided to the CRS research unit after an order from the study physician.

Storage

At the testing facility, all lorcaserin, placebo, and cocaine must be kept in a secure, locked storage place with access limited to authorized study personnel only. Lorcaserin bottles must be kept at room temperature (15°C–25°C) until ready for administration. Cocaine must be stored in accordance with regulations for controlled substances and per pharmacy policy.

Study Drug Accountability

An accurate and current accounting of the dispensing and return of study drug for each subject will be maintained on an ongoing basis by a member of the study site staff. The number of study drug dispensed and returned by the subject will be recorded on the Investigational Drug Accountability Record. The study staff must record an accurate accounting of each lorcaserin, and Cocaine/placebo dispensation and assignment number, as well as the date dispensed.

Both used and cocaine/placebo cassettes and IV cocaine vials must be accounted for on a drug disposition and accountability form, including the amount of cocaine that was not dispensed and was wasted from the 2mg/mL vial.

STUDY PROCEDURES AND GUIDELINES

A Schedule of Events representing the required testing procedures to be performed for the duration of the study is diagrammed in Appendix 1. While it will be preferable to schedule all of the study days consecutively, the modular design allows Day 1 and Day 2 to be scheduled independently in advance of the Day 3-7 and Day 8-12 study visits. The Day 3-7 and Day 8-12 hospital visits will be for 5 days each. In addition these 2 study visits may be scheduled separately to accommodate the availability of participants. However, all study days must be completed with a 90-day period. In the event that all study days are not scheduled consecutively, participants will be required to come into the research clinic for weekly monitoring (including UDS, vitals, and questionnaires).

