Procedure Afternoon Session	Cocaine Self Administration Depart from CRS			Three Doses of Cocaine (NexFin monitoring) Cardiovascular & Subjective Ratings Cardiac Biomarkers (4-6 hrs from last dose) Depart from CRS	Cocaine Self Administration Impulsivity Testing Depart from CRS
Study Drug	Placebo 8:00 a.m., Lorcaserin 10mg p.m. prior to departure or Placebo 8:00 a.m., Placebo p.m. prior to	Placebo 8:00 a.m., Lorcaserin 10mg p.m. prior to departure or Placebo 8:00	Placebo 8:00 a.m., Lorcaserin 10mg p.m. prior to departure or Placebo	Placebo 8:00 a.m., Lorcaserin 10mg p.m. prior to departure, or Placebo 8:00 a.m., placebo p.m. prior to departure	Placebo 8:00 a.m.

	departure	a.m., placebo p.m. prior to departure	8:00 a.m., placebo p.m. prior to departure		
--	-----------	--	---	--	--

Study Day	Day 8	Day 9	Day 10	Day 11	Day 12
Study Visit	Eight	Nine	Ten	Eleven	Twelve
Procedure Morning Session	Arrive at IDAS ECG	Arrive at IDAS ECG	Arrive at CRS ECG 10mg Cocaine for PK, Lorcaserin blood levels	Arrive at CRS ECG Cocaine Self Administration	Arrive at IDAS ECG Impulsivity Testing
Procedure Afternoon Session			Three Doses of Cocaine (NexFin monitoring) Cardiovascular & Subjective Ratings Cardiac Biomarkers (4-6 hrs from last dose) Impulsivity Testing Depart from CRS	Cocaine Self Administration Depart from CRS	Physical exam
Study Drug	Lorcaserin 10mg 8:00 a.m., Lorcaserin 10mg p.m. prior to departure. or Placebo 8:00 a.m., placebo p.m. prior to departure	Lorcaserin 10mg 8:00 a.m., Lorcaserin 10mg p.m. prior to departure or Placebo 8:00 a.m., placebo p.m. prior to departure	Lorcaserin 10mg 8:00 a.m., Lorcaserin 10mg p.m. prior to departure or Placebo 8:00 a.m., placebo p.m. prior to departure	Lorcaserin 10mg 8:00 a.m. or Placebo 8:00 a.m.,	

Self-Administration Session (Days 3, 7, and 11)

On days 3, 7, and 11, subjects participate in two self-administrative sessions and will make six choices for cocaine or \$5. The first session will begin at 10 am and the second at 1 pm (see Table 3 below), with each session being 2.5 hours long.

Table 3. Schedule of Cocaine Self Administration Procedure

Time	Choices	8 patients	8 patients
10:00 am	Baseline: VAS, BP/HR, EKG		
10:20 am	Choice 1	0 mg cocaine IV or \$ 5	25 mg cocaine IV or \$ 5
10:35 am	Choice 2	0 mg cocaine IV or \$ 5	25 mg cocaine IV or \$ 5

10:50 am	Choice 3	0 mg cocaine IV or \$ 5	25 mg cocaine IV or \$ 5
11:05 am	Choice 4	0 mg cocaine IV or \$ 5	25 mg cocaine IV or \$ 5

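### The self-administration ANOVA treats lorcaserin dose as a within-subject factor with no group or day term, so its dose effect cannot be told apart from study day

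*Combined protocol and SAP*

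**What the plan says.** Under Statistical Methods and Considerations, Analysis of Primary Endpoint, item 2 prescribes "Repeated measures ANOVA with cocaine dose (0mg, 25mg) and lorcaserin dose (0mg, 10mg, 20mg) as within subject factors". The synopsis and the Criteria for evaluation section carry the same text. A Bayesian analysis is added to this ANOVA.

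The design is described elsewhere:

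- **Groups.** Under Dosage/Dosage Regimen, Group A has placebo only and Group B has "placebo followed by an ascending dose of lorcaserin". The split is 6 to 12: "Six subjects will be assigned to Group A (placebo) and 12 subjects will be assigned to Group B (active lorcaserin").
- **Outcome days.** The Self-Administration section states: "On days 3, 7, and 11, subjects participate in two self-administrative sessions and will make six choices for cocaine" or money.
- **Dose at each session.** In Evaluations by Visit, both Day 3 sessions come before the first evening lorcaserin capsule. Group B is then at 10 mg a day up to the Day 7 sessions and at 10 mg twice daily from Day 8 to the Day 11 sessions.
- **Scheduling.** Study Procedures and Guidelines states "While it will be preferable to schedule all of the study days consecutively", but also that "these 2 study visits may be scheduled separately to accommodate the availability of participants". All study days must fall within 90 days.
- **Sample size.** Sample Size and Randomization uses a two-sample test on within-subject changes from baseline and picks the placebo n of 6 from it. The Bayesian model there has a treatment-group level, and of it the plan says: "This model is analogous to the repeated measures ANOVA except that prior information will be introduced".

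**The concern.** A within-subject dose factor with levels 0, 10 and 20 mg suits a trial in which every subject takes every dose in varied order. Here only Group B does so, in one fixed ascending order. The counterbalancing in the plan applies to the 0 and 25 mg cocaine sessions within a day, not to the order of lorcaserin doses.

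The placebo group, observed on the same three days, is the only means of separating drug from day, and item 2 does not use it. Practice, habituation, fatigue with the task or changed circumstances between visits would be credited to lorcaserin, or would cancel a real effect. Drift is plausible because the Day 3-7 block (0 and 10 mg sessions) and the Day 8-12 block (20 mg session) may be scheduled apart.

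Item 2 also leaves open whether the drug test is the lorcaserin main effect or the cocaine-by-lorcaserin interaction. The outcome sets the sample size, and the study is meant to inform phase II go/no-go decisions.

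**Working it through.** **1. The plan's own power figure.** The T-test row at n1 = 6, n2 = 12 gives 0.138, 0.528 and 0.981 at 10%, 25% and 50% change. Alpha, sidedness and SD are not stated; a two-sided 5% equal-variance test is assumed. Solving noncentral-t power for 0.528 gives a standardised difference of 1.080, so the SD of change is 25/1.080 = 23.1% of baseline. Scaling this to the other columns gives 0.129, 0.528 and 0.982, close to the stated row. The 25% and 50% cells of all three T-test rows give SDs from 22.0% to 24.9%. The row therefore behaves as a between-group test of change, which is not the item 2 ANOVA.

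**2. Aliasing.** Design matrix with subject effects, cocaine session, and the terms shown:

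| Data | Dose | Day | Dose and day |
|---|---|---|---|
| Group B only | rank 15 | rank 15 | rank 15 |
| All 18, received dose | rank 21 | rank 21 | rank 23 |

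In Group B, day adds nothing to dose, so the two are fully aliased. For all 18 subjects without a day term, a pure day shift of -0.5 (Day 7) and -1.0 (Day 11) with no drug effect returns dose coefficients of exactly -0.5 and -1.0. With day added, the dose coefficients are 0 and 0. If subject is a random intercept instead, the 20 mg coefficient is -0.941 for a -1.0 drift at assumed SDs of 1.5 between and 1.0 within subjects (-0.893 to -0.963 for within-subject SDs of 1.5 to 0.75). Coding Group A by session label as well makes dose identical to day.

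**3. Size on the power-table scale.** Let D be a linear Day 3 to Day 11 drift and S the SD of change. The three day shifts are 0, D/2 and D, with sum of squared deviations D²/2, and the residual variance is S²/2 under sphericity. For n = 12 the noncentrality is 12 × (D²/2)/(S²/2) = 12D²/S², on 2 and 22 df. At D = 10 and S = 23.1 this is 1200/533.6 = 2.25. Rejection rates with no drug effect:

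| Drift (% of baseline) | S = 23.1% | S from 24.9% to 22.0% |
|---|---|---|
| 0 | 0.050 | 0.050 |
| 5 | 0.089 | 0.083 to 0.093 |
| 10 | 0.222 | 0.20 to 0.24 |
| 25 | 0.889 | 0.83 to 0.92 |

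Masking: a true 25% reduction with an opposite 10% drift leaves a net 15%. The paired Day 11 versus Day 3 test in Group B then has noncentrality 15/(23.1/√12) = 2.25 on 11 df and rejects 0.54 of the time, against 0.93 without drift. The group contrast stays at 0.53.

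**4. Size in choices per session.** Simulation with 20,000 trials per cell, no drug effect, and assumed SDs of 1.5 between and 1.0 within subjects. Drift is in choices per session day:

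| Test | 0 | 0.1 | 0.25 | 0.5 |
|---|---|---|---|---|
| Group B, 25 mg sessions | 0.047 | 0.068 | 0.160 | 0.517 |
| All 18, received dose, subject blocks, 25 mg sessions | 0.046 | 0.068 | 0.160 | 0.493 |
| Lorcaserin main effect, both sessions drift | 0.050 | 0.083 | 0.285 | 0.828 |
| Cocaine-by-lorcaserin, only 25 mg sessions drift | 0.052 | 0.058 | 0.104 | 0.287 |

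If both sessions drift equally, the interaction stays at 0.048 to 0.050. The group t-test on change stays at 0.046 to 0.053 throughout. A separate simulation with drift from 0 to 1 residual SD held the dose test adjusted for day at 0.048 to 0.052.

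**The case against.** The strongest defence is that group was intended. The Bayesian model has a treatment-group level and is called the ANOVA's analogue apart from the prior; the power text is two-sample; and the VAS and IMT analyses compare lorcaserin with placebo subjects. On that reading item 2 merely lists its within-subject factors, and adding group gives an ordinary split-plot ANOVA. This may well be the intention, but item 2 does not say it, and it differs in wording from the VAS and IMT analyses.

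Several limits do stand:

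- The error rates depend on drift, for which the documents give no evidence. Separate scheduling makes drift plausible; it does not show it.
- If the drug test is the interaction and both cocaine sessions drift alike, the error rate is unaffected.
- The SD is back-solved. The 10% cells were left out because they are erratic (0.116 at n1 = 8 is below 0.138 at n1 = 6). Including them widens the SD range to about 22-28%; at 27.8% a 10% drift gives 0.165 rather than 0.222.
- Classical repeated-measures ANOVA would not normally accept Group A, which has no 10 or 20 mg cells, so the 18-subject variants matter less than the Group B result.
- The Bayesian analysis uses the placebo arm, and a separate SAP is promised: "The SAP will contain any modifications to the analysis plan described below". The first limits the harm and the second offers a place for the correction, but neither corrects the ANOVA.

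**Conclusion.** The concern holds. Followed as written, the first-named analysis of a primary outcome sets aside the randomised comparison that the sample size was built on. The aliasing of dose with day in Group B is algebraic and rests on no assumption. Its consequence is conditional: none without drift, and roughly a fourfold rise in false positives (0.222/0.05 = 4.4) if drift equals the plan's own low effect of 10%, assuming linear drift, sphericity and an SD of change near 23%. This is an incorrect specification and should be corrected before the analysis.

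**What to change.** Restate item 2 with group (A or B) between subjects; day (3, 7, 11) and cocaine session dose (0 or 25 mg) within subjects; and the group-by-day and group-by-day-by-cocaine-dose terms. Name one drug test: the Group B minus Group A difference in change from Day 3 in 25 mg-session choices, at one pre-specified day. The unadjusted change matches the form that was powered; ANCOVA on the Day 3 value is acceptable but is not that test. State which day and which cocaine session the power text's acute time point refers to. Report day contrasts within Group B as descriptive, not as dose-response. The choice of a single day is secondary; the group and day terms are essential.

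The cost is wording in the promised SAP, with no new data, plus a real loss of precision. The SE of the group difference in change is SD × √(1/6 + 1/12) = 0.500 SD, against SD/√12 = 0.289 SD within Group B, a ratio of √3 = 1.73 if both arms have the same SD. (It would be 1.22 or 2.35 if Group A's SD were 0.5 or 1.5 times Group B's.) T-test power for the group contrast is the plan's 0.138, 0.528 and 0.981 at 10%, 25% and 50% change. The paired test within Group B would show about 0.28, 0.93 and above 0.99, but those figures are valid only if drift is zero.
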